11.5 Ophthalmologic Examinations and Night Vision Questionnaire

A particular attention will be paid to ophthalmological safety, since fenretinide is known to cause a decrease in circulating vitamin A that may result in symptoms of nyctalopia, generally mild and rapidly reversible. In order to capture as much information as possible on ophthalmological TEAEs, ophthalmological assessments are performed at planned timepoints, and include both specific tests and use of a patient questionnaire. At screening, a Night Vision Questionnaire (NVQ) will be self-administrated, along with a full ophthalmological examination, and any abnormality will be recorded in the e-CRF. Clinically significant abnormalities may result in exclusion from the study, in particular low light vision abnormalities or dark adaptation abnormalities.

Moreover, the NVQ will be used according to the Schedule of Events, Section 2, to ask three (3) specific questions probing possible ophthalmological AEs. These questions will cover the following elements: Question 1: Dark adaptation difficulties; Question 2: Vision in condition of poor luminosity; Question 3: Recovery after dazzling. Results will be compared to previous occurrence to detect changes. Furthermore, possible ophthalmological AEs will be sought using non-suggestive questions at intermediate assessments done via phone calls. Details and specific questionnaire sheets are presented in the Study Reference Manual.

Proposed escalating safety monitoring of dark adaptation in planned Phase 2

Step 1: Night Vision Questionnaire (NVQ)

A specific questionnaire will be employed to assess the extent of reported symptoms and to trigger an escalation of objective assessments to determine if indeed the reported symptoms translate into a confirmed episode of nyctalopia. Also, a severity grading using CTCAE shall be used in order to qualify the confirmed episode of nyctalopia. The planned NVQ is presented below:

Question 1. Dark adaptation difficulties: In comparison with people around you, do you adapt easily to semi-obscurity when going from a bright to a dim environment, such as daylight to a movie theatre or tunnel.

Question 2. Vision in condition of poor luminosity: Are you able to perceive the outlines of objects in a domestic and semi-obscure environment, such in the indoor candlelight or poor streetlight, or to see the content of closets and kitchen cabinets?

Question 3. Recovery after dazzling: When you transition from a semi-obscure environment to a strongly lit one, do you remain dazzled?

Questions Q1 and Q2: Y (Yes) means normal. Questions Q3: N (No) means normal.

Assessment of the extent of reported symptoms: Level 0: no abnormal answer; Level 1: one abnormal answer; Level 2: two abnormal answers; and Level 3: three abnormal answers.

NVQ administration: Screening, Day 21, Day 77, Day 161, Day 189.

Level 1 NVQ will result in the given symptom to be considered a Grade 1 AE. However, it will not trigger an escalation to Step 2. Level 2 or 3 NVQ will automatically trigger a complete ophthalmological examination (Step 2) and its AE severity graded by the ophthalmologist.

Step 2: Complete ophthalmological examination, including specific dark adaptation tests

Administration: Screening, Day 77 and Day 189, and following any Level 2-3 NVQ report.

Suggested dark adaptation test to be included: a test able to evaluate dark-adaptation changes such as cone-rod break and the final rod threshold (see note below). Severity grading using CTCAE to be performed on confirmed nyctalopia episodes. If the reported symptoms do not get confirmed by the objective measures in Step 2, the default CTCAE severity Grade 1 will be used.

Step 3: Electroretinogram (ERG)

Administration: to be performed only if clinically indicated, in particular if the ophthalmological examination results are equivocal, or the type of signs/symptoms requires it.

Ophthalmologic examinations will be performed by (or under the oversight of) a licensed ophthalmologist at screening, Day 77 and Day 189 visits. It can also be triggered on demand if a patient reports signs of ophthalmologic nature upon questioning or at the time of the scheduled ophthalmologic questions posed on several occasions, according to the Schedule of Events, page 10.

The scheduled complete ophthalmologic examination will consist of the following: Examination of visual acuity, examination for amblyopia, examination of eyelids, conjunctiva, cornea, pupillary reactions to light and accommodation, low contrast visual function (Contrast Sensitivity), specific dark adaptation testsⁱⁱⁱ, lens,

ⁱⁱⁱ Specific Dark adaptation tests: May consist either of a dark adaptometry test performed with a dark adaptometer or equivalent **OR** a full field ERG test of the scotopic vision, and if possible the photopic vision, after dark adapting and light-adapting the patient, respectively. The order of testing may be done according to specific equipment in use.

vitreous humor, fundus examination of retina and retinal vessels, fundus visualization of optic nerve and macula.

The ad-hoc ophthalmologic examinations may differ since directed to potential medical condition based on the referral by the study Investigator. Such on-demand examinations should be recorded in detail, with results appended, in the proper unscheduled event e-CRF. The Medical Monitor should be notified of any additional ophthalmologic examinations.

The results of the post-study scheduled examination and any ad-hoc examination must be contrasted with the baseline ophthalmologic examination and any new adverse finding should be reported as an AE. Those that meet the definition of clinically significant assessment (see section 11.1.2 on clinically significant assessments) should be brought to the attention of the Medical Monitor, for forwarding to the DSMB.

The use of an ERG in lieu of the dark adaptometry test waives the need for further second line ERG testing, unless requested by the ophthalmologist. In extenuating circumstances such as the inability to locate the equipment to perform the above specific dark adaptation testing despite thorough feasibility assessments, such testing may be waived for a given clinical site. In all cases however, the site must have access, even distally, to an ERG in case a second line ERG examination is requested.

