Inclusions: Men and women 18 years and older, having a diagnosis of CF, Chronic CF lung disease with baseline FEV1 equal or superior to 40% predicted, stable at time of enrollment, Chronic pulmonary *Pseudomonas aeruginosa* colonization and/or infection.

Exclusions: Pregnant or breastfeeding women, inadequate contraception, presence of nyctalopia, other serious ophthalmological condition, serious dermatological conditions at enrolment, clinically abnormal liver or renal functions, history of gastrointestinal surgery or underlying gastrointestinal disorders of motility, and unstable intake of retinoids or lipid supplements.

Results and conclusions of the study

SAFETY RESULTS:

Overall, fenretinide was shown to be safe at all three doses studied for 21 days. The vast majority of adverse events (AEs) reported were mild, reversible with no sequelae, and without any action needed. Interestingly, the number of AEs in the active group decreased with the increase in fenretinide dosing. Many of these events were expected within the CF population studied, such as pulmonary exacerbations, characteristic of CF evolution, as well as reversible nyctalopia and dry skin which have been reported for fenretinide in other patient populations.

A particular attention was given to symptoms of nyctalopia. Fenretinide was shown to form reversible complexes with the circulating RBP, thus reducing the serum concentrations of retinol, an effect that may be associated with delayed dark adaptation in some patients. This is a well-documented and generally mild AE of fenretinide, as shown in previous clinical trials^{52, 54, 69, 70}. Moreover, it was shown to be fully reversible with treatment cessation and to be easily controlled by vitamin A supplementation and drug-free periods built within treatment regimens for chronic use.

However, because CF patients are known to be prone to vitamin A deficiency, their retinol levels and occurrence of ophthalmological AEs were closely monitored during the Phase Ib. The frequent probing of the patients about vision abnormalities resulted in a few referrals to the ophthalmologist but none of these reports resulted in objective measurements of nyctalopia or ophthalmologic abnormalities upon detailed examination. Also, the final ophthalmological examination did not reveal any abnormality or signs of retinal damage in these patients.

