Fenretinide has been safely administered in chemoprevention trials up to dose of 300 mg per day (1-1.5 μM plasma levels) for prolonged periods of time from 6 months to 5 years in large cancer populations with no significant toxicity^{69, 77, 78, 79, 80, 81}. Mild grade of nyctalopia and dermatologic disorders (dry skin, pruritus) were the most common side-effects of fenretinide treatment; rate of occurrence of both types of events tended to decrease with time or to recover spontaneously during the treatment period or shortly after cessation of dosing. Fenretinide plasma concentration (12 h post dose) at steady state was estimated to be $\sim 1 \mu\text{M}$ at 200mg dose and $\sim 1.5 \mu\text{M}$ at 300 mg dose. Adverse effects typical of other retinoids, such as decreased bone density, ligament calcification, and skeletal hyperostosis were not observed in these studies. Even after five years of therapy, abnormalities in night vision improved significantly after 7 days off therapy, and completely resolved one month after stopping fenretinide; plasma retinol concentrations returned to normal in one month following discontinuation of fenretinide^{80, 81}.

Single and repeat daily dose PK studies with fenretinide softgel formulation in healthy subjects and patient population indicate that fenretinide plasma exposure (C_{max} , AUC) also increased upon repeat daily dosing to reach a steady state level at 4-5 days^{82, 74, 83}. Presence of food increased significantly the plasma levels of the drug and has been used since as standard recommendation for fenretinide dosing⁷⁴. The increase in exposure was dose proportional up to 800mg. Plasma exposure on Day 21 with 300mg/day dose of LAU-7b formulation in adult CF patients was approximately equivalent to the exposure at the dose of 800mg on Day 28 in healthy adults with the softgel formulation, indicating an increase in fenretinide bioavailability by a factor of >2 with LAU-7b.

High-dose clinical trials

Phase I trials of high-dose (up to 14.5 μM plasma levels) oral fenretinide in pediatric solid tumors have been conducted with the corn-oil softgel formulation^{76, 79, 84}.

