11.1.1.1 Adverse Event Severity

The Investigator must determine and record the severity of all serious and non-serious AEs. The Common Terminology Criteria for Adverse Events (CTCAE), Version 4.03, (Cancer Therapy Evaluation Program website; available at: http://ctep.cancer.gov/protocolDevelopment/electronic_applications/ctc.htm ; accessed 01 December 2015) should be used for grading the severity of AEs. AEs of CTCAE Grades 4 and 5 should be documented as "life-threatening."

The severity of an AE that does not appear in the CTCAE scale should be determined according to the definitions below. Clinically significant laboratory tests should be recorded as AEs in the patient's source documents and e-CRF.

Severity will be assessed according to the following criteria:

Classification	Definition
Mild (Grade 1)	Mild level of discomfort and does not interfere with regular activities
Moderate (Grade 2)	Moderate level of discomfort and significantly interferes with regular activities

Severe (Grade 3)	Significant level of discomfort and prevents regular activities
Life-threatening (Grade 4)	Any adverse drug experience that places the patient, in the view of the investigator, at immediate risk of death

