3.10 Ophthalmologic Examinations and Night Vision Questionnaire

The answers to the NVQ questionnaires and the resulting levels will be summarized by treatment group. The results (normal/abnormal, new adverse findings) of the planned during- and post-study ophthalmologic examinations will be presented, alongside the baseline examination and summarized by treatment group. Ad-hoc examinations and findings will also be presented alongside the baseline examination. All reported symptoms of nyctalopia and hemeralopia will be tabulated by treatment group. Reported symptoms confirmed by objective measures will be tabulated separately by treatment group. Individual data will be presented in listings.

No statistical analyses of ophthalmologic data are planned

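### Night-vision adverse events fall under conflicting severity rules, and Protocol 11.5 ties the grade to test confirmation, so a moderate or severe symptom can be tabulated as Grade 1

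*Protocol*

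**What the plan says.** **General rule (Protocol 11.1.1.1).** "The Investigator must determine and record the severity of all serious and non-serious AEs". CTCAE 4.03 is the scale. A term absent from CTCAE is graded by discomfort and interference with activities; Grade 2, for example, is "Moderate level of discomfort and significantly interferes with regular activities". No exception is made for eye events.

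**Night-vision rule (Protocol 11.5).** The NVQ has three yes/no questions, and its level is the number of abnormal answers.
- Level 1: "Level 1 NVQ will result in the given symptom to be considered a Grade 1 AE", and no examination follows from it.
- Level 2 or 3: a complete ophthalmological examination is triggered and the ophthalmologist grades the event.
- CTCAE grading is reserved for confirmed nyctalopia. Otherwise: "If the reported symptoms do not get confirmed by the objective measures in Step 2, the default CTCAE severity Grade 1 will be used".
- If dark-adaptation equipment cannot be found despite a thorough search, "such testing may be waived for a given clinical site", although the site must still have access to an electroretinogram (ERG).

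**Visit instructions (Protocol 9.2.5).** The examination is triggered when Grade 2 severity is met, not NVQ Level 2.

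**Outputs.** SAP 3.18 describes treatment-emergent adverse events (TEAEs) by severity and tabulates them by maximal severity. Protocol 12.5.1 adds a separate listing of Grade 3-4 toxicities. SAP 3.10 summarises NVQ levels and tabulates all reported nyctalopia symptoms, and then: "Reported symptoms confirmed by objective measures will be tabulated separately by treatment group".

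**The concern.** Severity and objective confirmation are different attributes of an event. Section 11.5 makes the first depend on the second for the drug's best-documented adverse effect. A patient whose night vision seriously limits daily life is recorded as Grade 1 if only one question was answered abnormally, or if the examination did not confirm the report.

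The grade matters. Safety is co-primary (Protocol 7.1.2). SAP Section 5 removed Fisher's exact test and leaves adverse events to descriptive tables and qualitative evaluation, so the severity tables carry that part of the safety conclusion. The DSMB guidelines in Protocol 7.2.3 and 7.2.4 refer to severity as well as frequency of drug-related events. A reader of the maximal-severity table would take Grade 1 to mean mild, when for these events it may mean only that a test did not confirm them.

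**Working it through.** The plan gives no figure for night-vision events, so there is nothing to reproduce. The check compares the passages.

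**1. The three passages side by side.**

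| | 11.1.1.1 | 11.5 | 9.2.5 |
|---|---|---|---|
| Who grades | Investigator | Ophthalmologist for Level 2-3 | Not stated |
| Basis | CTCAE, or functional impact | Count of abnormal answers, then confirmation | A grade exists before the examination |
| Unconfirmed symptom | No special rule | Grade 1 | Not stated |
| Trigger for examination | Not addressed | NVQ Level 2 or 3 | Grade 2 or above |

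Grader and basis differ, and no section yields to another. The triggers differ too. A Level 1 report judged Grade 2 for its impact is examined under 9.2.5 but not under 11.5; a Level 2 report judged Grade 1 is the reverse. A report that is Grade 2 under 9.2.5 can be reset to Grade 1 by the examination it triggered.

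**2. Consequence for the tables.** Let *m* be the number of Level 2-3 reports that are moderate or worse in functional terms, and *c* the share confirmed. Under 11.5:

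reports shown at Grade 2 or above ≤ *c* × *m*; reports forced to Grade 1 = (1 − *c*) × *m*

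- *c* = 0: none of the *m* reports at Grade 2 or above.
- *c* = 0.5: at most half.
- *c* = 1: no forced loss.

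Level 1 reports contribute nothing at Grade 2 or above for any *c*. The number of patients with a nyctalopia TEAE does not depend on *c*. Neither *m* nor *c* is given for this trial. For the Phase Ib study, Protocol 5.4.4.1 says that after a few referrals "none of these reports resulted in objective measurements of nyctalopia or ophthalmologic abnormalities upon detailed examination", but without a denominator or the severity of the complaints.

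**3. Is failure to confirm good evidence of mildness?** Cycle *k* starts on Day 1 + 28(*k* − 1) and its last dosing day is Day 21 + 28(*k* − 1). For *k* = 1 this is Day 21; for *k* = 6 it is 21 + 140 = Day 161. Both are NVQ days without a scheduled eye examination, and both fall on the last dosing day of a cycle. No time limit is set for the examination they trigger. The next scheduled one after Day 161 is Day 189, 28 days later and off drug. Protocol 5.4.4.2 reports that in earlier long-term use "abnormalities in night vision improved significantly after 7 days off therapy", with complete resolution one month after stopping. A delayed examination may therefore find less than the patient experienced. Where the dark-adaptation test is waived, the most specific routine measure is also missing.

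**4. Can SAP 3.10 restore the grade?** No. Reported-symptom counts show frequency, and NVQ levels count abnormal answers; neither measures functional impact. The table of confirmed symptoms does not separate tested and negative from not tested.

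**The case against.** The strongest reply is that 11.5 is a deliberate, specific rule. For a subjective symptom that patients are repeatedly asked about, requiring objective confirmation and an ophthalmologist's grade is a defensible guard against over-grading, and a specific rule is usually read as displacing a general one. That reading would settle which rule applies, but the protocol does not state it, and the grade would still depend on confirmation rather than impact. The guard can be kept by reporting confirmation as its own attribute.

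A reader might infer more than the documents support:
- **That nyctalopia disappears from the safety tables.** It does not. It remains a Grade 1 TEAE, the primary safety objective is TEAE incidence, and all reported symptoms are tabulated whether confirmed or not.
- **That Level 1 patients are never examined.** All patients have complete examinations planned on Days 77 and 189, and examinations can be requested on demand. The point is only that Level 1 triggers none.
- **That waiver sites have no objective test.** The waiver is for extenuating circumstances, ERG access is mandatory, and the rest of the examination remains.
- **That night vision is back to normal within the drug-free week.** The source reports significant improvement at 7 days and full resolution at one month.
- **That the rule favours the active arm.** It applies blind to both arms. Nyctalopia is expected on LAU-7b, so more reports may be downgraded there; but if placebo complaints are confirmed less often, the rule could widen the contrast instead.
- **That the DSMB would be misled.** Its guidelines rest on judgement, frequency is unaffected, and it includes an ophthalmologist.

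It also stands that CTCAE's criteria for this term are not in the documents, so the exact grade under 11.1.1.1 is unknown. The difference in grader and in the role of confirmation does not depend on them.

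**Conclusion.** The concern holds for severity only. Three protocol sections disagree on who grades night-vision events, on what basis, and on what triggers the examination, with no order of precedence. Under the literal 11.5 rule a functionally moderate or severe symptom can be recorded as Grade 1 and be missing from the Grade 2 and above rows and from the Grade 3-4 listing. Incidence is unaffected.

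Neither the size nor the between-arm direction can be derived. The upper bound in the working assumes that 11.5 is followed as written; within it, the share of Level 2-3 reports that can reach Grade 2 or above runs from none to all. The Phase Ib experience shows that low confirmation is plausible but is too small and undescribed to predict a rate here.

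**What to change.** 1. **Protocol.** Reconcile 9.2.5, 11.1.1.1 and 11.5 so that one severity rule, not conditional on test confirmation, applies to night-vision events, and state who assigns the grade. Reconcile the Grade 2 and Level 2 triggers in the same clarification.
2. **SAP 3.18.** State that this grade feeds the severity and maximal-severity tables and the Grade 3-4 listing.
3. **SAP 3.10.** Report confirmation as a separate attribute by treatment group: confirmed, tested and not confirmed, or not tested, with days from last dose to test.

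The cost is a protocol clarification, a few lines in the SAP and one revised table layout. No examinations are added. The downside is that some subjective complaints will carry a higher grade; the confirmation column lets the reader see which ones.

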12 STATISTICAL ANALYSIS

A statistical analysis plan (SAP) will provide details of the methods of analysis to address all study objectives. The SAP may be amended during the course of the study, but will be finalized before the cutoff date for any analysis.

Data summaries by treatment group will be presented. For continuous variables, data will be summarized with the number of patients, mean, standard deviation, median, and minimum and maximum values by treatment group. For categorical variables, data will be tabulated in frequency tables to display the number and proportion of patients for each category by treatment group. Baseline assessments for each outcome variable will be defined as the last measurement obtained before the first dose of study drug except the baseline FEV₁ which will be the average of the screening and baseline best values, to reduce variability. Statistical significance will be set at the 5% level.

Diligent efforts will be made to prevent missing data in the study. For example, patients who discontinue the study treatment early or initiate medication changes (including those prohibited by the protocol) should still be followed for all regularly scheduled visits for safety and relevant efficacy assessments, or for a minimum of a 1-month follow-up. A clear distinction should be made between treatment discontinuation and study withdrawal. Efficacy assessments occurring after treatment discontinuation should not be included in the per-protocol analysis.

12.1 Sample Size Determination

The primary measure of efficacy is the absolute change in percent predicted FEV₁ from baseline to Week 24, fenretinide compared to placebo-treated patients. The sample size has been estimated for this endpoint.

A minimum of 136 adult CF patients will be randomized in this study. The following is calculated based on comparing changes in the parameter (compared to baseline) between groups:

FEV₁ % predicted (absolute change): The sample size was estimated according to the following assumptions:

- A t-test of the difference of the mean absolute change of FEV₁ of each group (active versus placebo) will be used;
- The FEV₁ data (absolute change) is normally distributed in each treatment group;
- The variance, expressed as SD is 8%;
- The clinical difference of interest (effect size) is 4%;
- The minimum statistical power of the t-test is 80% (0.8).

Below in Figure 6, are isotherms showing the required number of observations per treatment group (X-axis) as a function of the difference of interest (Y-axis) for different experimental assumptions of power (p) and SD (██████████ direct communication).

[figure not shown]

Figure 6: Isotherms of detectable significant differences as a function of sample size per treatment group (assuming a 1:1 randomization) under different assumptions of statistical power (p) and variance of FEV₁ % predicted (absolute change).

For the assumptions listed above, the solid blue line represents the applicable isotherm. Therefore, a **minimum of 60 completed patients per group** will be required to detect as significant a difference of 4% between fenretinide and placebo for FEV₁ % predicted (absolute change). While there will be patients that drop out after starting dosing, it is not expected to exceed 10%, hence the need to randomize 136 patients, a multiple of 8, due to the use of 3 stratification factors (2x2x2). The desired number of completers is also a multiple of 8.

More than 136 patients will be recruited to ensure that at least 136 patients start dosing. Patients who are withdrawn or lost to follow-up prior to baseline will be replaced to ensure at least 136 eligible patients start dosing.

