
Dose and Mode of Administration
	
 • Three (3) capsules of LAU-7b (300 mg total dose) or matching placebo (randomization 1:1) will be administered in the fed state with the first meal of the day (morning if possible) for 6 consecutive cycles consisting of 21 days on treatment followed by a 7-day treatment-free period. • Study treatment will be administered on top of current Standard of Care therapies.

Statistical Analysis
	
Sample size: A minimum of 136 CF patients will be randomized in this study. Sample size calculation is based on the primary efficacy variable, FEV₁ % predicted (absolute change) and on the following assumptions:

- A t-test of the difference of the mean absolute change in FEV₁ of each group (active versus placebo) will be used;
- The FEV₁ (absolute change) data is normally distributed in each treatment group;
- The FEV₁ variance, expressed as the Standard Deviation (SD) is 8%;
- The FEV₁ clinical difference of interest (effect size) is 4%;
- The minimum statistical power of the t-test is 80% (0.8);

A minimum of 60 completed patients per group will be required to detect as significant a difference of 4% between fenretinide and placebo for FEV₁ % predicted (absolute change).

Primary Efficacy Endpoint Analysis:

In the analysis for the primary efficacy endpoint, change from baseline in FEV₁ % predicted (absolute change), including all measurements up to Week 28 (both during and after treatment measurements, including after treatment discontinuation) will be analyzed based on a mixed-effect repeated-measure model. Even though no imputations will be used in the primary analysis, a sensitivity analysis will be conducted where missing data points will be imputed using appropriate interpolation methods; extrapolation methods will be used for truncated FEV₁ % predicted values.

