12.4 Efficacy Analysis

12.4.1 Analysis of Primary Endpoint

The study will be considered successful if a statistically significant advantage for fenretinide over placebo is obtained for the absolute change in FEV₁ percent predicted from baseline to Week 24.

Values for percent predicted FEV₁ as well as their change relative to baseline will be tabulated by time point and descriptive statistics will be used. In the analysis for the primary efficacy endpoint, change from baseline in FEV₁ % predicted (absolute change), including all measurements up to Week 28 (both during and after treatment measurements, including after treatment discontinuation) will be analyzed based on a mixed-effect repeated-measure model. Even though no imputations will be used in the primary analysis, a sensitivity analysis will be conducted where missing data points will be imputed using appropriate interpolation methods; extrapolation methods will be used for truncated FEV₁ % predicted values.

The planned model will include the absolute change from baseline in FEV₁ % predicted as the dependent variable; treatment, visit, and treatment-by-visit interaction as fixed effects; and patient as a random effect with adjustments for a) FEV₁ % predicted determined at the Screening/Baseline Visits (average where possible), b) PEx frequency in the prior year, and c) Co-administration or not of Kalydeco® (ivacaftor), Orkambi® (ivacaftor/lumacaftor), Symdeko® (ivacaftor/tezacaftor) or another commercially available CFTR modulator product. Additional post-hoc analyses may be performed in an exploratory manner depending on the frequency of other phenotypes or concomitant drugs. The primary result obtained from the model will be the treatment effect at Week 24. The estimated mean treatment effect, a 95% confidence interval, and a 2-sided P value will be generated. Alternative methods will be used if necessary due to data not meeting the standard requirements for the proposed analysis.

Full details will be specified in the SAP.

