3 STATISTICAL METHODS

3.1 Statistical Handling Policy

3.1.1 Analysis Conventions

This section details general guidelines to be used for the statistical analyses. Deviations from these general policies may be given in the specific detailed sections of this statistical analysis plan. When this situation occurs, the rules set forth in the specific section take precedence over the general conventions. The following policies will be applied to all data presentations and analyses:

- Two-tailed tests will be performed for all analyses that use statistical testing with a significance level of $\alpha = 0.05$
- All p-values will be rounded to 4 decimal places (SAS format p-value). All p-values that round to 0.000 will be presented as '<0.001' and p-values that round to 1.000 will be presented as '>0.999'.
- Summary descriptive statistics will consist of the number and percentage of responses in each category for discrete variables, and the mean, median, standard deviation (SD), minimum, maximum, and 95% confidence interval for continuous variables.
- All mean and median values will be formatted to one decimal place. Standard deviation values will be formatted to two decimal places.
- All percentages will be rounded to one decimal place. Where appropriate, the number and percentage of responses will be presented in the form XX (XX.X %), where the percentage is in the parentheses.
- All listings will be sorted for presentation in order of treatment group, site number, subject number, and date of procedure or event.
- When necessary for analysis purposes, partial dates will be completed (i.e., turned into complete dates) using the most conservative approach. Where appropriate, all analyses and summary tables will have the population sample size for each treatment group in the column heading.

- Tables will include titles with the corresponding analysis population and footnotes describing the analyses involved, and listings of covariates included in the analyses, where relevant.
- In order to maintain vertical alignment, all tables and listings will be incorporated into MS Word and an 8-point Courier New font will be used.
- Version 9.4 (or later) of SAS® will be the statistical software package used to produce all summaries, listings, statistical analyses, and graphs.
- Version 20.0 (or higher) of MedDRA will be used for adverse event and pre-treatment conditions coding.

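### Sixty completers per group give 77.5% power, not the stated minimum of 80%; on the plan's own assumptions 80% needs 64 per group.

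*Protocol*

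**What the plan says.** Protocol 12.1 lists the assumptions. On the test: "A t-test of the difference of the mean absolute change of FEV₁ of each group (active versus placebo) will be used". On variability: "The variance, expressed as SD is 8" (per cent). On the target: "The clinical difference of interest (effect size) is 4" (per cent). On power: "The minimum statistical power of the t-test is 80% (0.8"). SAP 2.6 carries the same list, and the Synopsis gives it in almost the same words. The conclusion, in the Synopsis wording, is: "A minimum of 60 completed patients per group will be required to detect as significant a difference of 4% between fenretinide and placebo".

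The 60 is read from a chart of isotherms (Protocol Figure 6, SAP Figure 2) that the public copies do not show. Protocol 12.1 then allows for dropout of no more than 10% and arrives at 136 randomized, chosen as a multiple of 8.

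The sample-size sections give neither alpha nor sidedness, but the plan fixes both elsewhere. Protocol 12 says "Statistical significance will be set at the 5% level". Protocol 12.4.1 says of the primary result "The estimated mean treatment effect, a 95% confidence interval, and a 2-sided P value will be generated". SAP 3.1.1 says "Two-tailed tests will be performed for all analyses that use statistical testing with a significance level of" 0.05.

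**The concern.** All the inputs to a two-sample t-test calculation are in the documents, so the 60 can be checked directly, and it does not follow from them. The plan calls both the power and the 60 a minimum, so a figure that falls short cannot be passed off as rounding.

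Absolute change in FEV₁ % predicted at Week 24 is the only success criterion (Protocol 12.4.1, SAP 3.2 and 3.14). If the result is null or borderline, readers will use the stated 80% power for 4 points to judge what the trial could have missed. That statement is too favourable on the plan's own terms.

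The 60 is also carried forward. The 136 is built on it, and the threshold of 57 patients per group for the multiple-imputation analysis in SAP 3.14.2 equals 0.95 × 60, so it appears to rest on the same number.

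**Working it through.** **Inputs.** Difference δ = 4, SD σ = 8, two-group t-test, power at least 0.80, 1:1 allocation and dropout of at most 10% (Protocol 12.1, SAP 2.6); alpha 0.05 (Protocol 12); two-sided (Protocol 12.4.1, SAP 3.1.1).

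**Formula.** With n completers per group, df = 2n − 2 and noncentrality λ = (δ/σ)·√(n/2) = 0.5·√(n/2). Power = P(|T| > t₀.₉₇₅,df), where T follows a noncentral t distribution with df and λ.

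**Attempt to reproduce 60.** At n = 60, df = 118, λ = 0.5·√30 = 2.739 and the critical value is 1.980. Power is 0.7753, so the stated figure is not reproduced.

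| n per group | λ | Power, two-sided t-test |
|---|---|---|
| 60 | 2.739 | 77.5% |
| 61 | 2.761 | 78.2% |
| 63 | 2.806 | 79.5% |
| 64 | 2.828 | 80.1% |
| 68 | 2.915 | 82.5% |

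The first n at or above 80% is 64.

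**Other readings that might give 60.**

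| Calculation | n per group for 80% | Power at 60 |
|---|---|---|
| Two-sided t-test | 64 | 77.5% |
| Two-sided normal approximation: 2·(8/4)²·(1.960 + 0.842)² = 62.8, rounded up | 63 | 78.2% |
| One-sided 5% t-test | 51 | 85.9% |
| One-sided 5% normal approximation | 50 | 86.3% |

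None of these gives 60.

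**What would make 60 correct.** Solving the same power equation for one input at a time, 80% at 60 per group needs a difference of 4.13, or an SD of 7.76, or a two-sided alpha of about 0.061.

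**Dropout step.** 120/0.9 = 133.3, so 134, raised to 136 as a multiple of 8. This step is consistent with its input. In the other direction, 136 × 0.9 = 122.4, about 61 per group, which gives 78.2%; the rounding up therefore does not restore 80%. Starting from 64 per group, 128/0.9 = 142.2, so 143, or 144 as a multiple of 8.

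**Missing data that 136 can absorb.** With 68 randomized per group, 80% holds only if at least 64 contribute a Week 24 value: 4/68 = 5.9% missing at most. With none missing, power is 82.5%.

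**The case against.** The strongest objection is that the t-test on completers is a planning simplification. The success criterion is a repeated-measures mixed model in the ITT population, adjusted for baseline FEV₁, prior exacerbations and CFTR modulator use (SAP 3.14). Covariates that explain part of the outcome reduce the residual SD. A residual SD of 7.76 is enough for 80% at 60 per group, which corresponds to a covariate–outcome correlation of √(1 − (7.76/8)²) ≈ 0.24. For assumed correlations of 0.10, 0.25 and 0.40, power at 60 per group is 77.9%, 80.1% and 84.2%.

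The 10% dropout is also a ceiling. Patients who stop treatment should still be followed, and their later measurements enter the primary analysis, so more than 60 per group may contribute at Week 24. Finally, the gap is only 2.5 percentage points or 4 completers per group, the figure came from a chart that cannot be inspected, and this is a Phase II proof-of-concept trial.

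Much of this stands as a limit on the consequence. The documents give no correlation, so they show neither that the mixed model falls below 80% nor that it reaches it. It does not rescue the 60: the plan justifies its size solely by the t-test on completers, claims no gain from covariates, and describes both the power and the 60 as minima.

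**Conclusion.** The point holds. Under the plan's own assumptions (two-group t-test, SD 8, difference 4, two-sided 5%, 1:1), 60 completers per group give 77.5% power and 80% needs 64 per group. The shortfall is 2.5 percentage points; put the other way, the difference detectable with 80% power is 4.13 points rather than 4. At the plan's dropout ceiling, the 136 randomized leave about 61 per group and 78.2%.

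This is an error in a stated planning figure on which the trial relies. It does not show that the adjusted mixed model is underpowered, since the documents do not allow that power to be worked out. Alpha and sidedness are taken from other sections of the same plan, which are explicit about both.

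**What to change.** Correct the statement in Protocol 12.1, the Synopsis and SAP 2.6. Suggested content: with SD 8 and a two-sided 5% t-test, 60 completers per group give 77.5% power for a 4-point difference, or 80% power for 4.13 points; 80% power for 4 points needs 64 completers per group. State alpha and sidedness in the same paragraph. If the sponsor expects the mixed model to recover the shortfall, the assumed covariate correlation and the resulting power should be written down.

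This is a wording change and does not require more patients. Its cost is a slightly less favourable power statement. The 136 is a stated minimum, so if enrolment goes beyond it the completer target should be 128 rather than 120; 128 is also a multiple of 8. Securing 128 completers at the full 10% dropout would take 143 randomized, or 144 as a multiple of 8. That is the sponsor's choice and is not needed to correct the text. The 57-patient threshold in SAP 3.14.2 should be checked at the same time, as it appears to derive from the 60.
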